4.1.5 Blinding and procedures for unblinding

4.1.5.1 Blinding

Double blind treatment period – Part 1 only

Patients, investigators and everyone involved in trial conduct or analysis will remain blinded with regard to the randomised treatment assignments during the double blind treatment period until Week 12 for each patient. The randomisation code for this trial period will be kept secret by Clinical Trial Support up to database lock of the preceding trial.

A trial independent statistician iSTAT will be assigned to prepare the summary reports for the DMC based on the agreed upon format and layout. All information, including adverse events, mortality, and laboratory parameters, will be provided in unblinded fashion. This will be

Page 36 of 84

accomplished by using coded labels and providing the DMC members with the decoding information separately.

Open label period – Part 1 and Part 2

Please refer to Section 3.1 for open label treatment assignment beginning at Week 12 for Part 1 and Day 1 for Part 2 and 3.2 for rationale. In the open label period of this trial, treatment allocation will not be concealed.

4.1.5.2 Unblinding and breaking the code

For the blinded period of this trial, emergency unblinding will be available to the investigator via IRT. It must only be used in an emergency situation when the identity of the trial drug must be known to the investigator in order to provide appropriate medical treatment or otherwise assure safety of trial participants. The reason for unblinding must be documented in the source documents and/or appropriate CRF page along with the date and the initials of the person who broke the code.

Due to the requirements to report Suspected Unexpected Serious Adverse Reactions (SUSARs), it may be necessary for a representative from BI's Pharmacovigilance group to access the randomisation code for individual patients during trial conduct. The access to the code will only be given to authorised Pharmacovigilance representatives and not be shared further.

4.1.6 Packaging, labelling, and re-supply

The investigational products will be provided by BI or a designated clinical research organisation (CRO). They will be packaged and labelled in accordance with the principles of Good Manufacturing Practice (GMP). Re-supply to the sites will be managed via an IRT system, which will also monitor expiry dates of supplies available at the sites. For details of packaging and the description of the label, refer to the ISF.

4.1.7 Storage conditions

Drug supplies will be kept in their original packaging and in a secure limited access storage area according to the recommended storage conditions on the medication label. Where necessary, a temperature log must be maintained for documentation If the storage conditions are found to be outside the specified range, the local clinical monitor (as provided in the list of contacts) must be contacted immediately.

4.1.8 Drug accountability

The investigator or designee will receive the investigational drugs delivered by the sponsor when the following requirements are fulfilled:

- Approval of the clinical trial protocol by the IRB/ethics committee,
- Availability of a signed and dated clinical trial contract between the sponsor and the investigational site,
- Approval/notification of the regulatory authority, e.g. competent authority,
- Availability of the curriculum vitae of the Principal Investigator,
- Availability of a signed and dated clinical trial protocol,

Page 37 of 84

• Availability of the proof of a medical license for the Principal Investigator,

• Availability of FDA Form 1572 (for US sites).

Investigational drugs are not allowed to be used outside the context of this protocol. They must not be forwarded to other investigators or clinics, if not site-to-site shipments are formally organized by the sponsor. Patients should be instructed to return unused investigational drug.

The investigator or designee must maintain records of the product's delivery to the trial site, the inventory at the site, the use by each patient, and the return to the sponsor or warehouse / drug distribution centre or alternative disposal of unused products. If applicable, the sponsor or warehouse / drug distribution centre will maintain records of the disposal.

These records will include dates, quantities, batch / serial numbers, expiry ('use- by') dates, and the unique code numbers assigned to the investigational product and trial patients. The investigator / pharmacist / investigational drug storage manager will maintain records that document adequately that the patients were provided the doses specified by the protocol and reconcile all investigational products received from the sponsor. At the time of return to the sponsor< and/or >appointed CRO, the investigator / pharmacist / investigational drug storage manager must verify that all unused or partially used drug supplies have been returned by the clinical trial patient and that no remaining supplies are in the investigator's possession.

4.2 OTHER TREATMENTS, EMERGENCY PROCEDURES, RESTRICTIONS

4.2.1 Other treatments and emergency procedures

Stable doses of concomitant therapies for chronic conditions, for which neither the condition nor the treatment are judged to exclude the patient from participation (cf. Section 3.3) may be permissible. All concomitant medications should be carefully evaluated by the Investigator and the Clinical Monitor Local (CML) should be contacted when there are questions regarding concomitant medications.

In the event that a patient experiences an intolerable increase of PsO during the course of the trial, the trial medication will be discontinued and anti-psoriatic agents may be used as rescue medications. Refer to Section 6.2.3 for early treatment and trial termination instructions.

In case of any AEs in need of treatment, symptomatic therapy according to investigator judgment will be permitted. All concomitant and/or rescue therapies will be recorded on the appropriate pages of the electronic case report form (eCRF).

Severe infections according to RCTC grading, serious infections, and opportunistic or mycobacterial infections:

Treatment of the infection should be initiated promptly according to local standard of care. Treatment with trial medication should be discontinued.

Clinical Trial Protocol Page 38 of 84

Malignancies

c22181693-04

In case of occurrence of malignant neoplasm other than appropriately treated basal cell carcinoma or squamous cell carcinoma of the skin or in situ carcinoma of uterine cervix, the investigator should discontinue treatment with the trial medication, and notify the CML. Diagnostics and treatment should be initiated according to local standard of care.

Suicidality

In case of signals of suicidal ideation the patient should be referred to a mental health professional for further work-up.

4.2.2 Restrictions

4.2.2.1 Restrictions regarding concomitant treatment

The medications, classes of medications, and foods listed in Table 4.2.2.1: 1 must not be taken for the time periods as specified. Classes of antipsoriatic medications listed in Table 4.2.2.1: 1 are likewise restricted, however may be permitted as rescue treatment, at the Investigator's discretion, if a patient experiences an intolerable increase of PsO during the course of the trial and the patient is undergoing early treatment and trial termination. In such cases, the Investigator must notify the BI CML and document the details of the drug used and reason in the eCRF. A comprehensive list of restricted medications can be found in the ISF.

Page 39 of 84

Table 4.2.2.1: 1 Restricted antipsoriatic medications, concomitant treatments and food

Medication or class of medications	Specified restriction time	
Drugs with known phototoxic or photoallergic potential (e.g., tetracyclines, fluorchinolones)	One week prior to randomisation in preceding study until EOO in this study	
Drugs or foods (e.g., seville oranges, grapefruit, paw paw and their products) which are known inhibitors or moderate or strong inducers of CYP3A, or are sensitive substrates of CYP1A2 CYP2B6, or CYP2C8, CYP2C9, or CYP2C19.	One week prior to randomisation in preceding study until EOO in this study	
Drugs with narrow therapeutic windows which are substrates of P-gp, BCRP, OATP1B1, OATP1B3, OAT3, OCT2, MATE1, and MATE2-K	One week prior to randomisation in preceding study through EOO in this study	
Investigational device or product (other than antipsoriatic drugs)	30 days prior to randomisationin preceding study through EOO in this study	
Any drug known to interfere with or to aggravate PsO including but not limited to lithium and interferons	4 weeks prior to randomisation in preceding study through EOO in this study	
BCG (Bacillus Calmette-Guérin) vaccine	1 year prior to randomisation in preceding study through 1 year after last administration of study drug in this study	
Investigational antipsoriatic drugs	12 weeks prior to randomisation in preceding study through EOO in this study	
Systemic anti-psoriatic medications or phototherapy	12 weeks prior to randomisation in preceding through EOO in this study	
Other systemic immunomodulating treatments (e.g. methotrexate, cyclosporine A, corticosteroids ¹), apremilast (Otezla®1,cyclophosphamide, tofacitinib (Xeljanz))	30 days prior to randomisation in preceding through EOO in this study	
¹ No restriction on corticosteroids with only a topical effect (e.g. inhalant corticosteroids to treat asthma or corticosteroid drops used in the eye or ear).		
Other systemic psoriasis treatments (e.g., retinoids, fumarates, any other drug known to possibly benefit psoriasis)	30 days prior to randomisation in preceding through EOO in this study	
Photochemotherapy (e.g., PUVA)	30 days prior to randomisation in preceding through EOO in this study	
Phototherapy (e.g., UVA, UVB)	2 weeks prior to randomisation in preceding through EOO in this study	

Page 40 of 84

Clinical Trial Protocol

Table 4.2.2.1: 1 (cont.) Restricted antipsoriatic medications, concomitant treatments and food cont'd

Medication or class of medications	Specified restriction time
Topical treatment for psoriasis or any other skin condition (e.g. corticosteroids², vitamin D analogues, vitamin A analogues, pimecrolimus, retinoids, salicylvaseline, salicylic acid, lactic acid, tacrolimus, tar, urea, andanthralin, α-hydroxy, fruit acids) ² Exception: Topical steroids of US class 6 (mild, such as desonide) or US class 7 (least potent, such as hydrocortisone) will be permitted for use limited to the face, axilla, and/or genitalia with a restriction of use within 24 hours prior to clinic visits where PASI is assessed	

4.2.2.2 Restrictions on diet and life style

The participants should take the medication after at least 6 hours fasting and should not eat for 30 minutes after drug administration.

Foods which are known strong or moderate inhibitors of CYP 3A (e.g., seville oranges, grapefruit, paw paw and their products) should be avoided during the study participation.

Moisturizers/emollients containing retinoids and the use of tanning beds are not allowed during the study.

Throughout their participation in the study, patients should avoid prolonged exposure to sunlight and artificial UV-light. When exposed to direct sunlight study participants should protect skin areas not covered by clothes by using sun-protection creams and lip balms with sun protection factor 30 or higher with protection against UV-A and UV-B. Patients should wear sunglasses when exposed to direct sun or other sources of UV-light. These protection measures must be applied until the end of the follow-up periods.

4.2.2.3 Contraception requirements

WOCBP (for the definition please refer to Section 3.3.2) must use highly effective methods of birth control per ICH M3 (R2) that result in a low failure rate of less than 1% per year when used consistently and correctly during the study, and for a period of at least 28 days after the last dose of study drug.

Highly effective methods include:

- Combined (estrogen and progestogen containing) hormonal birth control that prevents ovulation (oral, intravaginal, transdermal).
- Progestogen-only hormonal birth control that prevents ovulation (oral, injectable, implantable).
- Intrauterine device (IUD) or intrauterine hormone-releasing system (IUS).
- Bilateral tubal occlusion.
- Vasectomised sexual partner with documented absence of sperm.

c22181693-04

Clinical Trial Protocol

Page 41 of 84

Or WOCBP must abstain from male-female sex. This is defined as being in line with the preferred and usual lifestyle of the patient. Periodic abstinence, e.g., calendar, ovulation, symptothermal, post-ovulation methods; declaration of abstinence for the duration of exposure to study drug; and withdrawal are not acceptable.

4.3 TREATMENT COMPLIANCE

Patients are requested to bring all remaining trial medication including empty package material with them when attending visits.

Based on counts, treatment compliance will be calculated as shown in the formula below. Compliance will be verified by the Clinical Research Associate (CRA) authorised by the sponsor.

Treatment compliance (%) =
$$\frac{\text{Number of actually taken} \times 100}{\text{Number of which should have been taken}}$$

If the number of doses taken is not between 80-120%, site staff will explain to the patient the importance of treatment compliance.

Page 42 of 84

5. **ASSESSMENTS**

5.1 ASSESSMENT OF EFFICACY

The skin condition will be assessed by using the PASI and sPGA as described in Appendix 10.1 and 10.2 and the ISF.

5.2 ASSESSMENT OF SAFETY

5.2.1 Physical examination

A physical examination will be performed at the time points specified in the Flow Chart. It includes at a minimum general appearance, neck, lungs, cardiovascular system, abdomen, extremities, and skin.

Measurement of body weight will be performed at the time points specified in the Flow Chart.

The results must be included in the source documents available at the site.

5.2.2 Vital signs

Vital signs will be evaluated at the time points specified in the Flow Chart, prior to blood sampling. This includes systolic and diastolic blood pressure and pulse rate (electronically or by palpation count for 1 minute) in a seated position after 5 minutes of rest. The results must be included in the source documents available at the site.

5.2.3 Safety laboratory parameters

Safety laboratory parameters to be assessed are listed in Table 5.2.3: 1. For the sampling time points please see the Flow Chart.

All analyses will be performed by a central laboratory, the respective reference ranges will be provided in the ISF.

Blood samples for safety will be drawn prior to drug administration, under fasted conditions.

Instructions regarding sample collection, sample handling/processing and sample shipping are provided in the Laboratory Manual in the ISF.

The central laboratory will send reports to the investigator. It is the responsibility of the investigator to evaluate the laboratory reports. Clinically relevant abnormal findings as judged by the investigator will be reported as adverse events (please refer to Section 5.2.6).

In case the criteria for hepatic injury are fulfilled, a number of additional measures will be performed (please see Section 5.2.6.1 and the DILI Checklist provided in the ISF or

Page 43 of 84

Electronic Data Capture (eDC) system). The amount of blood taken from the patient concerned will be increased due to this additional sampling.

The central laboratory will transfer the results of the analysis to the sponsor.

Table 5.2.3: 1 Safety laboratory tests

Category	Test name
Haematology	Hematocrit (Hct)
	Hemoglobin (Hb)
	Glycosylated Hbc (HbA1c) ¹
	Red Blood Cell Count/ Erythrocytes
	Reticulocyte Count
	White Blood Cells / Leucocytes
	Platelet Count/ Thrombocytes
Diff. Automatic	Neutrophils (relative and absolute count)
	Eosinophils (relative and absolute count)
	Basophils (relative and absolute count)
	Monocytes (relative and absolute count)
	Lymphocytes (relative and absolute count)
Diff. Manual (if Diff Automatic is abnormal)	Neutrophils, bands (Stabs)
,	Neutrophils, polymorphonuclear (PMN)
	Eosinophils
	Basophils
	Monocytes
	Lymphocytes
Coagulation	Activated Partial Thromboplastin Time (aPTT)
	Prothrombin time (INR)
	Fibrinogen
Enzymes	AST(GOT)
•	ALT(GPT)
	Alkaline Phosphatase (AP)
	Creatine Kinase (CK)
	CK-MB, only if CK is elevated
	Gamma-Glutamyl Transferase (GGT/γ-GT)
	Lactic Dehydrogenase (LDH)
	Lipase
	Amylase
Electrolytes	Calcium
•	Sodium
	Potassium
	Chloride
	Bicarbonate

Only at Visit 1, Visit 5, Visit 9, Visit 13, Visit 17, Visit 21 and EOT Visit

Page 44 of 84

Table 5.2.3: 1 Safety laboratory tests Cont'd

Category	Test name
Substrates	Glucose
	BUN
	Uric acid
	Creatinine
	eGFR (estimated by CKD-EPI formula)
	Bilirubin Total
	Bilirubin Direct (if total is elevated)
	Bilirubin Indirect (if total is elevated)
	Troponin (reflex in case of elevated CK)
	Albumin
	C-Reactive Protein (CRP, High sensitivity)
	Cholesterol, total ¹
	Triglycerides ¹
	LDL-Cholesterol /HDL-Cholesterol ¹
Urine Pregnancy test (only for female patients of	Human Chorionic Gonadotropin in the urine
childbearing potential)	
Serum Pregnancy test (only if urine pregnancy test is	Human Serum Chorionic Gonadotropin
positive)	
Urinalysis with microscopic examination if urine	Urine Nitrite
analysis abnormal	Urine Protein
	Urine Glucose
	Urine Ketone
	Urobilinogen
	Urine Bilirubin
	Urine Blood
	Urine Leukocyte Esterase
	Urine pH
Urine	Albumin (quantitative)
	Creatinine
Infection testing	Hepatitis B Surface Antigen (qualitative) ¹
	Hepatitis C Antibodies (qualitative) ¹
	HIV-1 and HIV-2 Antibody (qualitative) ¹
10.1 (W. 2.1 W. 2.5 W. 2.0 W. 2.12 W. 2.17 W. 2.21	QuantiFERON®-TB ¹

¹Only at Visit 1, Visit 5, Visit 9, Visit 13, Visit 17, Visit 21 and EOT Visit

5.2.4 Electrocardiogram

ECGs will be read and evaluated centrally. The 12-lead ECGs will be recorded as scheduled in the Flow Chart. ECGs may be repeated for quality reasons and the repeated recording used for analysis.

If necessary, additional ECGs may be recorded for safety reasons.

The digital ECG recordings will be transmitted to a vendor for central evaluation and the results will be reported to the site.

Clinically relevant abnormal findings will be reported as AEs and will be followed up and/or treated as medically appropriate.

c22181693-04 Page 45 of 84

5.2.5 Other safety parameters

5.2.5.1 Suicidality

Suicidal thoughts and behavior will be assessed by the C-SSRS (R08-1147).

The C-SSRS is a semi-structured, investigator-rated interview, developed by clinical experts in cooperation with the FDA, assessing both suicidal behavior and suicidal ideation. It does not give a global score, but provides some categorical and some severity information specifically for behavior and ideation.

The C-SSRS interview may be administered by any type of physician, psychologist, clinical social worker, mental health counselor, nurse, or coordinator with C-SSRS training. It has a typical duration of five minutes, and causes only a low burden on subjects. At a minimum, the interview consists of 2 screening questions related to suicidal ideation and 4 related to suicidal behavior, and may be expanded to up to 17 items in case of positive responses. Free text entries are allowed for; the investigator has to directly evaluate the scale and write a report. In this trial paper forms will be used for the assessment of the C-SSRS® and results will be transcribed into the e-CRF.

The C-SSRS has been widely used in large multinational clinical trials. The C-SSRS was administered at Visit 1 of 1407-0030 (using the 'baseline' screening' version) with the aim to exclude patients with active moderate or severe symptomatology within a specified time prior to the screening or screening visit of that trial. The lifetime and past year history of suicidal ideation and behavior was also recorded in 1407-0030.

After the screening visit, the assessment 'since last visit' version was performed at each visit of 1407-0030 and will be administered at each visit of this extension trial. The investigator is to review positive and negative reports for plausibility and clinical relevance. Doubtful reports may be repeated or reports may be validated by a consulting psychiatrist or other mental health professional expert. If there is a confirmed positive report of suicidal behavior or suicidal ideation type 4 or 5 after start of trial, the investigator is to immediately interview the patient, and/or is to consult a mental health professional. If the positive report is confirmed, appropriate actions for the patient's safety have to be initiated.

All C-SSRS reports of suicidal ideation type 4 or 5 and all reports of suicidal behavior must be reported as separate SAEs by the investigator.

For 'Self-injurious behavior, without suicidal intent', standard AE / SAE reporting rules are to be applied.

For each negative report (suicidal ideation type 1, 2 or 3) after the start of the trial, the investigator is to decide based on clinical judgment whether it represents an Adverse Event (AE) as defined in the protocol, and if it is considered an AE then it must be reported accordingly.

Major Adverse Cardiovascular Event (MACE) 5.2.5.2

An independent adjudication committee will be used to adjudicate all observed cardio- and cerebro-vascular and thrombotic events reported during the conduct of the study to assure consistent assessment of MACE. See Section 8.7.

Page 46 of 84

5.2.6 Assessment of adverse events

5.2.6.1 Definitions of AEs

5.2.6.1.1 Adverse event

An AE is defined as any untoward medical occurrence in a patient or clinical investigation subject administered a medicinal product and which does not necessarily have to have a causal relationship with this treatment.

An AE can therefore be any unfavourable and unintended sign (including an abnormal laboratory finding), symptom, or disease temporally associated with the use of a medicinal product, whether or not considered related to the medicinal product.

The following should also be recorded as an AE in the CRF and BI SAE form (if applicable):

- Worsening of the underlying disease or of other pre-existing conditions
- Changes in vital signs, ECG, physical examination and laboratory test results, if they are judged clinically relevant by the investigator.

If such abnormalities already exist prior to trial inclusion, they will be considered as baseline conditions and should be collected in the eCRF only.

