3.3.4.1 Discontinuation of trial treatment

An individual patient may be withdrawn from trial treatment if:

- The patient wants to discontinue trial treatment, without the need to justify the decision.
- The patient has repeatedly shown to be non-compliant with important trial procedures and, in the opinion of both, the investigator and sponsor representative, is not willing or able to stick to the trial requirements in the future.
- The patient experiences an intolerable increase of PsO, the trial medication will be discontinued and anti-psoriatic agents may be used as rescue medications (refer to Section 4.2.1).
- The patient needs to take concomitant drugs that interfere with the investigational product as listed in Table 4.2.2.1: 1.
- The patient can no longer be treated with trial medication for other medical reasons (such as surgery, adverse events, other diseases, or pregnancy).
- The patient develops suicidal ideation of type 4 or 5 in the C-SSRS (i.e., active suicidal thought with intent but without specific plan, or active suicidal thought with plan and intent). The patient should immediately be referred to a mental health professional for further work-up.
- In addition to these criteria, the physician may discontinue subjects at any time based on his or her clinical judgment.

In case of a temporary reason, trial treatment should be restarted as early as possible if medically justified.

Page 32 of 84

Even if the trial treatment is permanently discontinued, the patient remains in the trial and, given his/her agreement, will undergo the procedures for early treatment discontinuation, follow up, and vital status collection as outlined in the Flow Chart and Section 6.2.3.

For all patients, the reason for withdrawal from trial treatment (e.g. adverse events) must be recorded in the CRF. These data will be included in the trial database and reported.

If a patient becomes pregnant during a trial, the study medication needs to be discontinued. The patient will be followed up until birth or otherwise termination of the pregnancy. The data of the patient will be collected and reported in the clinical trial report (CTR) until last patient visit and any events thereafter will be reported in the BI Pharmacovigilance database.

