7.3.4 Safety analyses

Adverse events will be coded using the Medical Dictionary for Drug Regulatory Activities (MedDRA). Standard BI summary tables and listings will be produced. All adverse events with an onset between start of treatment and end of the REP, a period of 7 days after the last dose of trial medication, will be assigned to the on-treatment period for evaluation.

All treated patients will be included in the safety analysis. In general, safety analyses will be descriptive in nature and will be based on BI standards. No hypothesis testing is planned.

Statistical analysis and reporting of adverse events will concentrate on treatment-emergent adverse events, i.e. all adverse events occurring between start of treatment and end of the REP. Adverse events that start before first drug intake and deteriorate under treatment will also be considered as 'treatment-emergent'.

Exposure-adjusted adverse event incidence rates (per the primary endpoint) will be calculated using the following approach:

• The incidence rate (per 100 subject years) of a selected adverse event (also known as the incidence density rate or person-time incidence rate) is defined as the number of subjects experiencing the adverse event per treatment group during the time at risk divided by the total time of subjects at risk in that treatment group to contribute an event to the analysis multiplied by 100 (per 100 subject years), where:

Time at risk [subject years] = (date of onset of AE – study drug start date + 1) / 365.25

If, for a subject, no treatment emergent adverse event occurred, then the time at risk will be censored at the minimum of (date of death; drug stop date + 28 days; last contact date).

For each AE, the incidence rate will therefore be calculated as:

Incidence rate [per 100 subject years (pt-yrs)] = 100 * number of subjects with TEAE / Total TEAE-specific time at risk [subject years].

Exact 95% confidence intervals (CI) around the observed AE incidence rate will also be provided.

Page 58 of 84

Frequency, severity, and causal relationship of adverse events will be tabulated by system organ class and preferred term after coding according to the current version of the Medical Dictionary for Drug Regulatory Activities (MedDRA) at database lock.

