7.4 PRIMARY ENDPOINT(S)

7.4.1 Primary analysis of the primary endpoint(s)

The primary endpoint is the occurrence of treatment emergent adverse events (TEAEs) up to Week 288. The primary analysis will be based on the exposure adjusted rate of patients reporting a treatment emergent adverse event (TEAE) up to Week 288.

Exposure-adjusted adverse event incidence rates will be calculated using the following approach:

- The incidence rate (per 100 subject years) of a selected adverse event (also known as the incidence density rate or person-time incidence rate) is defined as the number of subjects experiencing the adverse event per treatment group during the time at risk divided by the total time of subjects at risk in that treatment group to contribute an event to the analysis multiplied by 100 (per 100 subject years), where for each subject and each TEAE preferred term:

$$\text{Time at risk [subject years]} = (\text{date of first onset of AE} - \text{study drug start date} + 1) / 365.25$$

If, for a subject, no treatment emergent adverse event occurred for the preferred term, then the time at risk will be censored at the minimum of (date of death; drug stop date + 7 days; last contact date).

- For each AE, the incidence rate will therefore be calculated as:

$$\text{Incidence rate [per 100 subject years (pt-yrs)]} = 100 * \text{number of subjects with TEAE} / \text{Total TEAE-specific time at risk [subject years].}$$

Exact 95% confidence intervals (CI) around the observed AE incidence rate will also be provided using exact Poisson regression.

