7.8.1 Adverse Events

The analyses of adverse events will be descriptive in nature. All analyses of AEs will be based on the number of patients with AEs (not the number of AEs).

Unless otherwise specified, the analyses of AEs will be descriptive in nature. All analyses of AEs will be based on the number of subjects with AEs and NOT on the number of AEs.

The analysis of AEs will be based on the concept of treatment emergent AEs. That means that all AEs occurring between first drug intake till 7 days after last drug intake will be assigned to the received treatment. All AEs occurring before first drug intake will be assigned to 'screening' and all AEs occurring after last drug intake + 7 days will be assigned to 'follow-up' (for listings only). For details on the treatment definition, see [Section 6.1](#).

According to ICH E3 [\(5\)](#), in addition to Deaths and serious adverse events, 'other significant' AEs need to be listed in the clinical trial report. These will be any non-serious adverse event that led to an action taken with study drug (e.g. discontinuation or dose reduced or interrupted). An overall summary of adverse events will be presented.

The frequency of subjects with AEs will be summarised by treatment, primary system organ class and PT using the version of MedDRA at the database lock. Separate tables will be provided for subjects with SAEs, AEs leading to treatment discontinuation and related AEs.

The system organ classes will be sorted by default by decreasing frequency and PTs will be sorted by decreasing frequency within SOC.

For further details on summarization of AE data, please refer to the guideline 'Handling and summarization of adverse event data for clinical trial reports and integrated summaries' [\(4\)](#).

The severity of AEs will be summarised by the maximum intensity of the events each patient had (as indicated by the recorded RCTC version 2 grade). This will show the number and percent of patients who had at most mild, moderate, severe, and life threatening events. Severe adverse event is defined as an AE with RCTC grade equals to 3 (severe) or 4 (life threatening).

Groupings of adverse events and adverse events of special interest (AESI)

The AESI have been defined in the protocol.

Other user-defined special adverse event grouped term for BI 730357 specified in the following [Table 7.8.1:1](#).

Table 7.8.1: 1 User Defined Adverse Event Group Terms

N	Term	Definition #

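### Psoriasis worsening is recorded as an adverse event, so the pooled safety totals by dose mix loss of efficacy with tolerability; a supplementary version without those terms is needed

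*Protocol*

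**What the plan says.** **Recording.** Protocol 5.2.6.1.1 states: "The following should also be recorded as an AE in the CRF". The list that follows includes "Worsening of the underlying disease or of other pre-existing conditions". It sets no severity or PASI threshold and makes no exemption for events that are also efficacy outcomes.

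**Stopping.** Protocol 3.3.4.1 lists among the reasons for withdrawal from treatment: "The patient experiences an intolerable increase of PsO, the trial medication will be discontinued". Section 4.2.1 repeats this: "In the event that a patient experiences an intolerable increase of PsO during the course of the trial, the trial medication will be discontinued".

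**Counting.** Protocol 7.3.4 defines treatment-emergent events as "all adverse events occurring between start of treatment and end of the REP", plus earlier events that deteriorate under treatment. Psoriasis terms are not excluded. SAP 7.4.1 says: "The primary analysis will be based on the exposure adjusted rate of patients reporting a treatment emergent adverse event (TEAE) up to Week 288". The formula beneath it, however, defines time at risk "where for each subject and each TEAE preferred term".

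**Tables.** SAP 7.8.1 counts patients, not events. It plans an overall summary and separate tables for AEs leading to discontinuation, other significant AEs and worst RCTC grade. On other significant AEs it says: "These will be any non-serious adverse event that led to an action taken with study drug". Table 7.8.1: 1 has five user-defined groups, none of them for psoriasis worsening. SAP 6.1 plans a combined Part 1 and Part 2 set by dose at onset, with columns for 25, 50, 100, 200 and 400 mg.

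**The concern.** A patient whose psoriasis flares and who stops drug for it can be counted as having a TEAE, an AE leading to discontinuation and, if the event is non-serious, an other significant AE. The secondary time-to-loss endpoints already measure the same loss of response. Where worsening differs between doses, the pooled safety totals differ too, even with identical tolerability.

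The preferred-term tables will show psoriasis as its own row, but that row does not repair a patient-count total. A patient may have both psoriasis worsening and another event, so subtracting the row does not give the number of patients with any other event. In a time-to-first-TEAE rate, a flare that comes first also ends the patient's time at risk.

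The trial tests no hypothesis, and long-term safety is its main output. Descriptive totals by dose are what readers will take from it.

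**Working it through.** The documents give no AE rate, discontinuation rate or worsening rate by dose, so there is no plan figure to reproduce. **Every rate below is an assumption**, in events per 100 patient-years.

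**Method.** The SAP rate is 100 × patients with the event / time at risk. With constant hazards, the rate to first event of either kind is the psoriasis rate plus the non-psoriasis rate.

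**(a) AEs leading to discontinuation.** Assume non-psoriasis stops of 3 (100 mg) and 6 (400 mg), a true ratio of 6/3 = 2.0.

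| Psoriasis stops, 100 vs 400 mg | Total, 100 mg | Total, 400 mg | Ratio 400/100 |
|---|---|---|---|
| 2 vs 1 | 3 + 2 = 5 | 6 + 1 = 7 | 1.40 |
| 3 vs 1 | 3 + 3 = 6 | 6 + 1 = 7 | 1.17 |
| 4 vs 1 | 3 + 4 = 7 | 6 + 1 = 7 | 1.00 |
| 6 vs 1 | 3 + 6 = 9 | 6 + 1 = 7 | 0.78 |
| 3 vs 3 | 3 + 3 = 6 | 6 + 3 = 9 | 1.50 |
| 1 vs 4 | 3 + 1 = 4 | 6 + 4 = 10 | 2.50 |

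The difference can be attenuated, cancelled, reversed or inflated. Equal psoriasis rates still dilute it. With psoriasis stops left out, the ratio is 2.0 in every row.

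**(b) Any TEAE.** Assume non-psoriasis rates of 100 (100 mg) and 130 (400 mg), ratio 1.30.

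- Psoriasis 5 vs 2: 132/105 = 1.26
- 10 vs 2: 132/110 = 1.20
- 20 vs 5: 135/120 = 1.125
- 40 vs 5: 135/140 = 0.96

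The total moves little unless worsening is frequent. Crude percentages do not help. Week 288 is 288 × 7/365.25 = 5.52 years, and 1 − exp(−1.00 × 5.52) = 99.6% even at the lowest rate assumed here. The exposure-adjusted total is then the informative one.

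**(c) A single preferred-term row.** A simulation used 400,000 patients per setting, a true nausea rate of 8, psoriasis hazards of 1, 5 and 20 with half of the cases stopping drug, and other stopping at 10. It returned 8.03, 7.99 and 8.00. If events are independent, psoriasis stops do not distort other terms' rows.

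**Direction.** The documents point both ways.

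- *More worsening at lower doses:* the rationale for Global Amendment 3 (Protocol 11.3) calls 100 mg sub-optimal, and Protocol 3.1 calls 400 mg the anticipated therapeutic dose.
- *More worsening at 400 mg:* Part 1 patients needed at least PASI50 at Week 24 of 1407-0030, whereas Part 2 patients may enter on perceived improvement at Week 12 (Protocol 3.3.2). Part 2 may include former placebo patients (3.2), and its entry may be delayed by up to 16 weeks (3.1). The option to move from 100 to 200 mg may take poorly controlled patients out of the 100 mg column.

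**The case against.** **The primary rate is per preferred term.** This stands. Under the SAP 7.4.1 formula psoriasis is its own row and leaves the others intact. Only a pooled any-TEAE rate is affected, and 7.4.1 does not clearly say whether one will be shown, although its opening sentence reads that way.

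**A 400 mg signal would still be seen.** A reader might infer that the recording rule makes less effective doses look less safe and hides intolerance at 400 mg. The documents do not support that. AEs are tabulated by system organ class and preferred term, gastric intolerance and gastritis are AESIs, and gastritis terms form a user-defined group. Only a reader relying on totals could be misled, and the direction is not established.

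**Not every psoriasis stop need be an AE stop.** This partly stands. Protocol 3.3.4.1 lists an intolerable increase of psoriasis separately from adverse events as a reason, and SAP 7 summarises discontinuation by reason. The recording wording is also *should*, not *must*. How such a stop is coded depends on CRF conventions that are not shown. Double counting is possible, not certain.

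**Other documents may cover it.** SAP 7.8.1 defers to an AE summarisation guideline and to Safety SAP updates, neither of which is available. A psoriasis group may be planned there, but nothing visible says so.

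**Little is at stake.** There is no test and no randomisation, and Protocol 3.2 concedes that no powered or controlled analysis is possible. This limits the severity. The combined dose columns are planned all the same and will be read side by side.

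**Conclusion.** The concern holds for the pooled totals only. Recording disease worsening as an AE is neither an error nor a contradiction, and the per-preferred-term primary analysis is sound on this point. The totals for any TEAE, severe AEs, other significant AEs and AEs leading to discontinuation can mix efficacy loss with tolerability, and the visible plan has no version that separates them.

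The size is unknown. Against an assumed true discontinuation ratio of 2.0, the pooled 400/100 mg ratio ran from 0.78 to 2.5. For any TEAE, an assumed 1.30 became 1.26 to 0.96. These figures rest on invented rates, constant hazards and the assumption that psoriasis stops are coded as AEs leading to discontinuation. They show that the totals can be ambiguous, not which way they will lean. This is a cheap improvement to a descriptive safety report, not a flaw that invalidates it.

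**What to change.** 1. In SAP Table 7.8.1: 1 add a user-defined group, psoriasis worsening, with its preferred terms fixed before any results by dose are reviewed. A list chosen later would be post hoc.
2. Show any rebound after stopping drug as its own line. It is arguably a drug-safety outcome and should not disappear with the exclusion.
3. For the pooled any-TEAE exposure-adjusted rate and for the overall, severe, other-significant and discontinuation totals by dose, add a supplementary version without the group beside the planned version.
4. Base pooled dose-related safety statements on both versions.

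AE collection, the per-preferred-term primary analysis and every planned table stay unchanged. The cost is a short term list, a few lines of SAP text and a few extra tables.
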